Glycemic variability (GV), which refers to daily glucose fluctuations, including preprandial, postprandial glycemia, and hypoglycemic episodes, could be associated with an increase in oxidative stress and the development of microvascular complications in Type 2 Diabetes (T2D). Although SGLT2 inhibitors have been shown to reduce GV, there is no evidence regarding their effect in newly diagnosed T2D patients when used at the initiation of pharmacological therapy, nor regarding their impact on oxidative stress.

Main objective: To evaluate the effect of dual therapy with Dapagliflozin + Metformin (DAPA/MET) versus Metformin monotherapy (MET) over 12 weeks on GV in patients with T2D.

Secondary objectives: To evaluate the effects on HbA1c, insulin, plasma antioxidant capacity, body composition, and cardiometabolic risk factors.

Hypothesis: The reduction in glycemic variability (measured using the mean amplitude of glycemic excursions, MAGE) will be greater in patients receiving dual therapy with Dapagliflozin + Metformin compared to those receiving Metformin monotherapy.

Methods: 88 patients with T2D without catabolic symptoms or complications, with HbA1c >7.5% and <12% and BMI >25 kg/m² will be included. Patients will be randomized 1:1 to receive Dapagliflozin 10 mg/day + Metformin 2000 mg/day (n=44) or Metformin 2000 mg/day (n=44). GV will be measured with the iPro™ CGM system (Medtronic) at baseline and the end of the 12 weeks of treatment.

Statistical analysis: The primary dependent variable will be MAGE as a marker of GV. Other variables such as HbA1c, serum insulin, plasma antioxidant capacity, VCAM-1, and adiponectin will be analyzed. Change deltas will be calculated for each group and compared using ANCOVA. A p-value ≤0.05 will be considered significant. All analyses will be performed with SPSS 20.0.

Background

There is growing evidence regarding the beneficial effects of sustained intensive glycemic control on the incidence and progression of complications in T1D and T2D [1]. HbA1c has been the main marker used to define glycemic control because it provides an average of glycemia in the 2 or 3 months before its measurement, with the American Diabetes Association recommending that HbA1c levels be maintained between 6.5% and <8%, depending on the individual characteristics of each patient [2]. Although HbA1c is a standardized, validated, and evidence-based marker, it is not useful for evaluating glycemic fluctuations over short periods [1].

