HbA1c reflects the mean glucose concentration over the last 8 to 12 weeks. It is well documented that elevated HbA1c levels are associated with an increased risk of diabetes complications. However, evidence has shown that glycemic variability, particularly MAGE, is associated with greater vascular endothelial dysfunction and oxidative stress, consequently increasing the risk of developing retinopathy, nephropathy, and coronary artery disease. A frequently used measure of GV is MAGE, which reflects the mean of the differences between consecutive peaks and nadirs of blood glucose concentrations and is therefore independent of the mean glucose level [47]. Correcting GV is currently considered a clinical objective to reduce average glycemia and determine its direct effects on vascular complications in diabetes. Sodium-glucose cotransporter type 2 inhibitors have been shown to be effective in improving glycemic control, in terms of fasting glycemia, glycated hemoglobin, and glycemic variability determined by MAGE. However, the evidence primarily considers their use in Type 2 Diabetes patients diagnosed more than 5 years prior and previously treated with other pharmacological regimens, including insulin. Therefore, the effect of SGLT2i on glycemic variability and oxidative stress when used in patients with a recent diagnosis of Type 2 Diabetes is unknown.

10. Justification

Type 2 Diabetes is one of the most prevalent chronic diseases worldwide and constitutes the eighth leading cause of death and disability due to its micro and macrovascular complications. Chronic hyperglycemia, through the production of advanced glycation end products, induces a proinflammatory cascade involving mainly Interleukin 6, Tumor Necrosis Factor-alpha, and the formation of free radicals, such as superoxide and hydrogen peroxide. This generates a state of oxidative and mitochondrial stress, causing irreversible damage to cell membranes and interfering with various cellular signaling pathways, representing the main pathophysiological mechanism for the development of microvascular complications. For this reason, the current treatment of Diabetes focuses primarily on reducing exposure to hyperglycemia, and intensive glycemic control has been shown to decrease the risk of microvascular complications, especially if implemented early after diagnosis.

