STATISTICAL ANALYSIS. Quantitative variables with normal distribution according to the Kolmogorov-Smirnov test will be expressed as Means \pm Standard Deviation. Quantitative variables with non-normal distribution will be expressed as Medians (Interquartile Range 25-75). Categorical variables will be expressed as proportions (percentages). Change deltas will be calculated for each group and compared using ANCOVA, considering age, sex, BMI, baseline HbA1c, and time since Diabetes diagnosis as covariates. A p-value \leq 0.05 will be considered significant. All analyses will be performed with SPSS 22.0.

Study Timeline

Study Type	Select an option
Retrospective	
Prospective	X

Process of assigning study groups

Maneuver	Yes (Include corresponding information)	No	Not applicable
Randomization	X		
Open-label study	X		
Single-blind study		X	
Double-blind study		X	
Triple-blind study		X	

Description of maneuvers or interventions

- **Clinical History:** Will be conducted via telemedicine (Phone call/Videocall, Whatsapp, Teams, Zoom, Google Forms) at visit 1 DP of the treatment period.
- **Diet Plan Prescription:** Will be conducted via telemedicine (Phone call/Videocall, Whatsapp, Teams, Zoom, Google Forms) at visit 2 DP of the treatment period.
- **Anthropometric Measurements and Physical Exam:** Will be performed at visits 1 DP, 3 DP, 4 DP, and 6 DP of the treatment period.
- **GV Monitoring:** Both groups will be monitored before treatment and at the end. The iPro™ CGM system (Medtronic, Northridge, CA) will be used. Baseline continuous glucose monitoring will begin in week 1 (Visit 1DP) and end seven days later at Visit 2DP (day 1, Week 2). End-of-treatment continuous glucose monitoring will begin at Visit 5 DP (week 12) and end 7 days later (Visit 6 DP).
- **Measurement of HbA1c and Insulin Levels:** Will be performed at visits 1DP and 6DP of

the treatment period.

- **Spot Urine Sample:** Will be collected at Visits 1DP, 3DP, 4DP, and 6DP.
- **Measurement of Oxidative Stress and Inflammation Biomarkers:** Will be performed at visits 1DP, 3DP, 4DP, and 6DP of the treatment period.
- **WHO Physical Activity Questionnaire:** Will be evaluated via telemedicine (Phone call, Whatsapp, Teams, Zoom, Google Forms) at visits 1DP, 3DP, 4DP, and 6DP of the treatment period.

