Definition of Follow-up Variables

- **Primary Variable:** Change from baseline in GV (MAGE) in mg/dL after 12 weeks of treatment between the DAPA+ MET group versus the MET monotherapy group.
- **Secondary Variables:**
 - Change from baseline (absolute difference) in HbA1c levels (%) after 12 weeks of treatment between the DAPA + MET group versus the MET monotherapy group.
 - Change from baseline (total difference) in insulin levels (μ U/mL) after 12 weeks of treatment between the DAPA + MET group versus the MET monotherapy group.
 - Change from baseline (absolute difference) in oxidative stress measurement (total antioxidant capacity) after 12 weeks of treatment between the DAPA + MET group versus the MET monotherapy group.
 - Change from baseline (total difference) in the measurement of inflammation biomarkers (VCAM-1 and adiponectin) after 12 weeks of treatment between the DAPA + MET group versus the MET monotherapy group.
 - Change from baseline (absolute difference) in body fat quantification after 12 weeks of treatment between the DAPA + MET group versus the MET monotherapy group.
 - Change from baseline (total difference) in the parameters of cardio-metabolic risk factors (weight (kg), total cholesterol (mg/dL), HDL (mg/dL), LDLc (mg/dL), albuminuria (mg/mg creatinine), and blood pressure (mmHg)) after 12 weeks of treatment between the DAPA + MET group versus the MET monotherapy group.

Methods for Data Collection

Electronic Record containing the clinical history collected via telemedicine (Phone call/Videocall, Whatsapp, Teams, Zoom or Google Forms), information gathered at each visit, notes containing patient physical examinations, physical activity questionnaires answered via telemedicine (Phone call/Videocall, Whatsapp, Teams, Zoom or Google Forms), Nutrition notes collected via telemedicine (Phone call/Videocall, Whatsapp, Teams or Zoom), and laboratory results. Patients will only be identified by their initials, date of birth, and the internal protocol folio number.

Monitoring and Auditing Procedures During Study Development

Not applicable

Criteria for Failure and Success

- **Failure:** No decrease in GV in the DAPA + MET group compared to the MET monotherapy group.
- **Success:** A decrease in GV in the DAPA+ MET group compared to the MET monotherapy group.

Sample Size

The sample size was determined using the difference of means formula:

$$n = (Z\alpha / 2 + Z\beta)^2 * 2 * \sigma^2 / d^2,$$

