A reduction in glucose variability from 4.85 to 2.2 was estimated with an expected standard deviation of 2.8 in the MAGE index (values based on the study by R. R. Henry et al., "Effects of Dapagliflozin on 24-Hour Glycemic Control in Patients with Type 2 Diabetes: A Randomized Controlled Trial," *Diabetes Technol. Ther.*, vol. 20, no. 11, pp. 715–724, Nov. 2018.), with an alpha value of 0.05 and a power of 0.80, resulting in a sample size of 88 subjects, with 44 subjects in each treatment group. No adjustments were included in the sample size calculation to estimate the subjects required for the estimated differences in secondary variables.

Description of techniques, devices, and/or instruments to be used (Including special mechanical, electronic, cybernetic equipment)

Continuous glucose monitoring will be performed using the iPro™2 Continuous glucose monitor, from Medtronic®, to determine the MAGE value as follows:

- **Calculation of Mean Amplitude of Glucose Excursion (MAGE):**
 - In the first step, all local maximum/minimum values are determined.
 - The next step is an evaluation of maximum/minimum pairs against the standard deviation (SD).
 - If the difference from minimum to maximum is greater than the SD, this variation from the mean measurement is retained.
 - If the local maximum/minimum is less than 1 SD, it is excluded from further calculations.
 - These channels are retained and summed to achieve the MAGE
- Glycated hemoglobin (HbA1c) will be measured using HPLC (Variant II Turbo, Biorad).
- Insulin levels will be measured with Access-2 equipment (Beckman Coulter, Inc.).
- Oxidative stress will be measured with the BioAssay Systems antioxidant assay kit (DTAC-

100) (QuantiChrom Antioxidant Assay Kit) (BioAssay Systems).

- VCAM-1 will be measured using ELISA kits (Merck Millipore, USA).
- Adiponectin measured using ELISA kits (Merck Millipore, USA).
- Body fat quantification by bioelectrical impedance with the Jawon scale, model⁵ IOI 353 - JMW160.
- Anthropometric variables will be measured using standardized techniques; these include height, weight, waist, and hip circumferences.
- BMI will be calculated using the equation: weight / height² (kg/m²).
- Blood pressure will be measured considering the mean of two determinations after sitting for at least 5 minutes.
- Mean arterial pressure (MAP) will be calculated with the formula: (systolic blood pressure * 0.33) + (diastolic blood pressure * 0.66).

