- Change from baseline (total difference) in the measurement of inflammation biomarkers (VCAM-1 and adiponectin) after 12 weeks of treatment between the DAPA + MET group versus the MET monotherapy group.
- Change from baseline (absolute difference) in body fat quantification after 12 weeks of treatment between the DAPA + MET group versus the MET monotherapy group.
- Change from baseline (total difference) in the parameters of cardio-metabolic risk factors (weight (kg), total cholesterol (mg/dL), HDL (mg/dL), LDLc (mg/dL), albuminuria (mg/mg creatinine), and blood pressure (mmHg)) after 12 weeks of treatment between the DAPA + MET group versus the MET monotherapy group.

Methods to be used to contact patients

Personal contact data such as landline and mobile phone numbers, email address will be obtained via Phone call/Videocall, Whatsapp, Teams, Zoom, or Google Forms. Due to the SARS-CoV-2 pandemic, investigators will conduct home visits and/or collect data and hold medical consultations via Phone call/Videocall, Whatsapp, Teams, Zoom, or Google Forms.

Statistical Analysis (Description of the information processing and presentation plan. Include justification for the statistical tests to be used)

Stratified randomization in both groups to balance patient types and control potential bias. The normality of variables will be analyzed using the Kolmogorov-Smirnov test. According to the distribution of variables, they will be expressed as mean and standard deviation (SD) or median and interquartile range (IQR) for normally or skewed distributed variables, respectively. GV will be determined using the MAGE index. Comparison between the two groups will be evaluated using ANCOVA. A p-value based on two-tailed tests ≤ 0.05 will be considered significant. All analyses will be performed with SPSS 20.0 (Chicago, IL). Patients experiencing an acute stress event during the study will be excluded from the analysis due to the impact on GV.

Justification of sample size (include study power and the p-value considered significant)

The sample size was determined using the difference of means formula:

$$n = (Z\alpha / 2 + Z\beta)^2 * 2 * \sigma^2 / d^2,$$

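### The planned ANCOVA of change in MAGE leaves out baseline MAGE, which costs precision and leaves the estimate exposed to chance baseline imbalance

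*Protocol*

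**What the plan says.** The primary variable, in Definition of Follow-up Variables and again in section 39, is "Change from baseline in GV (MAGE) in mg/dL after 12 weeks of treatment". Baseline MAGE is available: under GV Monitoring, "Both groups will be monitored before treatment and at the end", and the SAP confirms a 7-day CGM recording at each time.

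The model appears in three places in the Protocol:

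- **Summary, Statistical analysis:** "Change deltas will be calculated for each group and compared using ANCOVA". No covariates are named.
- **Methods, STATISTICAL ANALYSIS:** the changes are "compared using ANCOVA, considering age, sex, BMI, baseline HbA1c, and time since Diabetes diagnosis as covariates". This is the only covariate list in the documents.
- **Statistical Analysis (main section):** "Comparison between the two groups will be evaluated using ANCOVA". No covariates are named. The same paragraph announces "Stratified randomization in both groups to balance patient types and control potential bias", but names no stratification factors and does not say whether any enter the model.

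The SAP text as supplied repeats the sample size and reports recruitment, patient flow and baseline results. It gives no model for the primary comparison. The t and Mann-Whitney tests that it names follow directly on the baseline results and seem to belong to Table 1.

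**The concern.** An unadjusted change score fixes the slope of week-12 MAGE on baseline MAGE at 1. With measurement noise and ordinary within-patient variation, the true slope is normally below 1. Two things follow when baseline MAGE is left out of the model.

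First, variance that baseline MAGE would explain stays in the residual, and the confidence interval is wider than it needs to be. Second, a chance difference between arms in baseline MAGE is over-corrected: with no treatment effect at all, the arm that starts higher shows the larger fall.

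Baseline HbA1c is in the model but is only a partial substitute. The Protocol itself (section 9, Problem Definition) says that MAGE "is therefore independent of the mean glucose level".

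The same gap affects the secondary outcomes whose own baseline is not listed: insulin, antioxidant capacity, VCAM-1, adiponectin, body fat, lipids, albuminuria and blood pressure. HbA1c is not affected, and weight is largely covered by baseline BMI.

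**Working it through.** **Inputs from the documents.** Completers 41 and 39 (SAP). Expected fall from 4.85 to 2.2, so d = 2.65, with an "expected standard deviation of 2.8 in the MAGE index" (Protocol, Sample Size); two-sided alpha 0.05, power 0.80, 44 per arm.

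**The plan's own figure.** (1.960 + 0.842)² × 2 × 2.8² / 2.65² = 17.5, so 18 per arm, not 44. That is a separate matter and nothing about the covariates rests on it. It does mean that the power figures in step 4 hold only for the stated inputs. Those inputs carry no unit, whereas the endpoint is in mg/dL and the Background cites a MAGE decrease of 15.3 mg/dL.

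**Assumptions (not in the documents).** r = correlation of baseline with week-12 MAGE, 0.3 to 0.7, with 0.8 also shown. h = correlation of MAGE with HbA1c, 0.3 to 0.5. k = week-12 SD divided by baseline SD, taken as 1 unless stated. HbA1c carries no further information on week-12 MAGE once baseline MAGE is known, and the other four covariates are unrelated to MAGE.

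**1. Precision.** In units of the baseline variance:

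- planned model: V₁ = (1 − kr)²(1 − h²) + k²(1 − r²)
- with baseline MAGE added: V₂ = k²(1 − r²)

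Example, k = 1, r = 0.5, h = 0.3: V₁ = 0.25 × 0.91 + 0.75 = 0.978; V₂ = 0.75; ratio 0.767.

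Results for k = 1, as h = 0.3 / h = 0.5:

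| r | V₂/V₁ | SE reduction | Shift for a 0.5 SD imbalance (SD) |
|---|---|---|---|
| 0.3 | 0.671 / 0.712 | 18% / 16% | 0.319 / 0.262 |
| 0.5 | 0.767 / 0.800 | 12% / 11% | 0.228 / 0.188 |
| 0.7 | 0.862 / 0.883 | 7% / 6% | 0.137 / 0.113 |
| 0.8 | 0.908 / 0.923 | 5% / 4% | 0.091 / 0.075 |

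A sixth covariate with n = 80 costs a factor 72/71 = 1.014. The net ratios are then 0.681 to 0.896 for r = 0.3 to 0.7, and 0.921 / 0.936 at r = 0.8. With equal SDs the gain disappears only at r = 0.970 (h = 0.3) or 0.963 (h = 0.5).

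Unequal SDs:

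- k = 0.8: ratio 0.526 (r = 0.3, h = 0.3) to 0.703 (r = 0.8, h = 0.5), so the SE is 27% to 16% smaller.
- k = 1.2: ratio 0.779 (r = 0.3, h = 0.3), SE 12% smaller. At r = 0.8, h = 0.5 the ratio is 0.998, and 0.998 × 1.014 is about 1.01, a net loss of about 1%.

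**2. Imbalance.** A baseline difference of s SD shifts the planned estimate by (1 − kr) × s × (1 − h²), in favour of the arm that starts higher. With k = 1, s = 0.5, r = 0.3, h = 0.3: 0.7 × 0.5 × 0.91 = 0.319 SD. The last column of the table gives the other cells. With baseline MAGE in the model the expected shift is zero.

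Under simple randomisation the SD of a chance imbalance is √(1/41 + 1/39) = 0.224. An imbalance of at least 0.5 SD in either direction therefore has probability 0.025, and stratification could lower it.

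**3. Simulation.** With 41 and 39 patients, five covariates, no treatment effect and 6,000 runs per cell, both models rejected in 4.6% to 5.4% of runs. At s = 0.5 the planned estimate shifted by −0.317 to −0.075 SD over the cells; the estimate adjusted for baseline MAGE shifted by 0.00.

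**4. Power at the stated inputs.** Noncentral t, d = 2.65, residual df 73 (planned) and 72 (adjusted), lowest value over the cells for k = 1:

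| Reading of 2.8 | Planned | With baseline MAGE |
|---|---|---|
| SD of MAGE | 94.8% | 99.2% |
| SD of change | 98.7% | 99.3% |

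**The case against.** The strongest reply is that little is at stake. The planned analysis is unbiased over randomisations, holds its error rate and already adjusts for five covariates. On the stated inputs its power is at least 94.8%. No imbalance in MAGE is shown: the SAP's time-in-range difference (p=0.02) concerns another measure, and Table 1, which may give baseline MAGE by arm, is not in the supplied text. A 0.5 SD imbalance has a probability of only about 2.5%. All of this stands, and it limits the weight of the point.

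The size of the gain also rests on assumed correlations, and on a slope kr below 1. That stands too. If the week-12 SD is 20% larger than baseline, break-even after the covariate cost comes at r of about 0.74 to 0.75, and at r = 0.7 a 0.5 SD imbalance shifts the estimate by only 0.06 to 0.07 SD.

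Another objection is that citing MAGE as independent of mean glucose sits badly with an assumed MAGE-HbA1c correlation of 0.3 to 0.5. Taking h = 0 strengthens the point: for r = 0.3 to 0.7 the variance ratio becomes (1 + r)/2 = 0.65 to 0.85.

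High power on the stated inputs gives limited reassurance, because those inputs have no unit and do not reproduce the sample size. Interval width and protection from imbalance matter at any power.

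Finally, the supplied SAP text is incomplete, so its silence proves nothing about the full SAP. That is right. The point rests on the Protocol's covariate list, which names one baseline value, HbA1c, and not that of the primary endpoint.

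**Conclusion.** The concern holds and should be fixed. The only covariate list omits the baseline value of the primary endpoint, which is already collected in both arms, and nothing in the supplied text adds it.

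Under the equal-SD assumptions, with r from 0.3 to 0.7, the cost is a standard error that could be 6% to 18% smaller, and a shift of 0.11 to 0.32 SD should a 0.5 SD baseline imbalance occur. At r = 0.8 these fall to 4% to 5% and 0.08 to 0.09 SD. If the week-12 SD is larger than baseline and r is high, there is nothing to gain and about 1% in variance to lose.

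The omission is certain; its size depends on correlations that the documents do not give. This is a matter of efficiency and robustness, not of validity. On the stated inputs it is not mainly a matter of power; if the true effect is smaller or the SD larger, the lost precision would count for more.

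**What to change.** State one model, in the same words, in the Summary, in Methods (STATISTICAL ANALYSIS), in the main Statistical Analysis section and in the SAP: ANCOVA of week-12 MAGE (or its change) on arm, baseline MAGE, the five listed covariates and any factors used to stratify the randomisation, which should be named. Report the adjusted difference with its 95% CI. For each secondary outcome, add its own baseline where it is not already in the model. Report baseline MAGE by arm if Table 1 does not already do so.

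Timing decides the status of this model, because the SAP reports that follow-up had finished in an open-label trial:

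- **If the change is dated and shown to precede access to week-12 outcomes,** and is sent to the research committee by the Protocol's route for deviations from the statistical plan, make the new model primary and keep the present one as a sensitivity analysis.
- **Otherwise,** keep the present model primary and report the baseline-adjusted one beside it, labelled as added later.

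The SAP's dates cannot settle this as they stand: the last patient is recruited in December 2021, yet the study ends in March 2021. Correct them and give the date of first access to week-12 data.

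The cost is one degree of freedom for each added baseline covariate (about 1.4% in variance; any stratification factors would add their own) and one letter to the committee. No new data are needed. The main risk, a post-hoc switch of the primary model, is met by the order above.

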- **Food Record:** Will be performed at visits 1 FP, 2 FP, 1 DP, 2 DP, 3 DP, 4 DP, 5 DP, and 6 DP of the treatment period. The patient will keep a daily record, and data will be collected via Phone call/Videocall, or e-mail.

Table of Times and Events

Procedure	Visit 1 FP	Visit 2 FP	Visit 1 DP	Visit 2 DP	Visit 3 DP	Visit 4 DP	Visit 5 DP	Visit 6 DP
	Week -2	Week -1	Week 0	Week 1	Week 5	Week 9	Week 12	Week 13
Informed Consent			x					
Weight and Height			x		x	x		x
Pre-randomization Inclusion Criteria*	x							
Clinical History			x					
MET Tolerance Evaluation		x						
Inclusion and	x							

Exclusion Criteria								
Anthropometric Measurements (weight, waist circ., blood pressure)			x		x	x		x
Physical Exam			x		x	x		x
Concomitant Diseases	x							
Concomitant Medications	x							
Glycemic Assessment Monitoring			x				x	
CGM Removal				x				x
WHO Physical Activity Questionnaire	x		x		x	x		x
Food Record (Consumed Diet Assessment)	x		x	x	x	x	x	x
HbA1c Levels			x		x			x
Fructosamine					x	x		
Insulin Levels			x		x	x		x

Oxidative Stress			x		x	x		x
Inflammation Biomarkers			x		x	x		x
Body Fat Quantification			x		x	x		x
Nutritional Counseling and Food Plan				x				

FP: Off-protocol, DP: On-protocol, MCG: Continuous Glucose Monitoring

* Determination of HbA1c levels and BMI

** Lipids (total cholesterol, HDL, LDLc, triglycerides), glucose, ALT, AST, creatinine, creatinine clearance, uric acid, albuminuria)

Treatments (if applicable) (include a table for each study medication)

Medication 1

Item	Include corresponding information	No	Not applicable
Name	Dapagliflozin		
Does it comply with "Good Manufacturing Practices"?	Yes		
Codes, labeling, storage, retention, and safeguarding of drug samples	Yes		
Pharmaceutical form	Tablets of 10 mg		
Dose	1 tablet		

Administration interval	Every 24 hours		
Route of administration	Oral		
Administration speed	Immediate, with a glass of water		
Duration of treatment	12 weeks		

Medication 2

Item	Include corresponding information	No	Not applicable
Name	Metformin		
Does it comply with "Good Manufacturing Practices"?	Yes		
Codes, labeling, storage, retention, and safeguarding of drug samples	Yes		
Pharmaceutical form	Tablet 1000 mg Tablet 500 mg		
Dose	1 tablet of 1000 mg or 2 tablets of 500 mg		
Administration interval	Every 12 hours		
Route of administration	Oral		
Administration speed	Immediate, with a glass of water		
Duration of treatment	12 weeks		

Follow-up

Item	Include corresponding information	No	Not applicable

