## Statistical Analysis Plan

The sample size was determined using the mean difference formula:  $n = (Z\alpha / 2 + Z\beta) 2 * 2 * \sigma^2 / d^2$  a reduction in GV was estimated from 4.85 to 2.2 with an expected standard deviation of 2.8 in the MAGE index according to RR. Henry et al. [19] with an alpha value of 0.05 and a power of 0.80, resulting in a sample size of 88 subjects, with 44 subjects in each treatment group.

Patient recruitment began in October 2019 and was interrupted due to the SARS-COV-2 pandemic in March 2020. Nevertheless, patients who were already enrolled were followed up. Recruitment was normally restarted in March 2021; one of the inclusion criteria was adjusted, allowing HbA1c <13.0%, prior limit <12.0%. The last patient was recruited on December 6th, 2021. The complete study was concluded in March 2021.

A total of 88 patients met the selection criteria, signed the informed consent, and were randomized 1:1 on [www.randomization.com](http://www.randomization.com) (complete list of it is showed as supplementary material) to receive daily either DAPA 10 mg + MET 2000mg or MET 2000mg for 12 weeks. Both groups were monitored for GV using a CGM system for 7 days at baseline (W0) and on week 12 (W12).

Pre-randomization: patients were given 2000mg of MET daily for two weeks, only patients who tolerated this dose were included in the study and a treatment was randomly assigned.

Treatment: subjects who met the pre-randomization period and tolerated treatment were randomized 1:1 to receive either DAPA 10 mg/day + MET 2000 mg/day or MET 2000 mg/day for 12 weeks.

Of the total of 264 patients surveyed, a sample of 88 met the inclusion criteria and none of the exclusion criteria randomization DAPA+MET n=42 and MET n= 46. During the study, 7 patients discontinued (DAPA+MET n=1 and MET n=6). 80 patients concluded the study for 12 weeks (DAPA+MET n=41 and MET n=39). One patient was removed from the study (MET n=1) because he did not comply his medication intake nor the instructions during CGM. Study flowchart is displayed in Figure 1.

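### Several secondary endpoints are measured at weeks 5 and 9, but the plan compares only a baseline-to-end change with no missing-data rule, while non-completion was 15.2% with MET and 2.4% with DAPA+MET

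*Protocol*

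**What the plan says.** **Schedule.** In the protocol's description of maneuvers, the anthropometric line reads "Will be performed at visits 1 DP, 3 DP, 4 DP, and 6 DP of the treatment period". The line for oxidative stress and inflammation biomarkers names the same four visits. In the Table of Times and Events, visit 1DP is week 0 and visits 3DP to 6DP are headed "Week 5 Week 9 Week 12 Week 13". The rows "Anthropometric Measurements (weight, waist circ., blood pressure") and "Body Fat Quantification" are marked at 1DP, 3DP, 4DP and 6DP, so at weeks 0, 5, 9 and 13.

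**Endpoints.** Every secondary variable is a two-point change, for example "Change from baseline (absolute difference) in body fat quantification after 12 weeks of treatment" (protocol, Definition of Follow-up Variables, repeated under Outcomes and Variables).

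**Analysis.** The protocol's Methods section says "Change deltas will be calculated for each group and compared using ANCOVA", with age, sex, BMI, baseline HbA1c and time since diagnosis as covariates. The later Statistical Analysis section again names ANCOVA. The SAP mentions only Student's t test and the Mann-Whitney U test, directly after its baseline characteristics. Neither document has a repeated-measures model, a use for the week-5 and week-9 values, a defined analysis population or a rule for missing data.

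**Patient flow.** The SAP states: "During the study, 7 patients discontinued (DAPA+MET n=1 and MET n=6"). One further MET patient was removed for not following medication intake and the CGM instructions. Of 42 DAPA+MET and 46 MET patients randomised, 41 and 39 completed.

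**Primary endpoint.** For glycemic variability, "Both groups will be monitored before treatment and at the end". There is no interim CGM.

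**The concern.** A change score needs a final value. Without one, and with no rule to supply it, the patient has nothing to enter into the comparison, even if two on-treatment values were recorded. This matters because non-completion was about six times as frequent in one arm, and the trial is open-label, so staying in could depend on perceived response.

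A completers-only change analysis is unbiased only if non-completion is unrelated to outcome given the covariates. Those covariates contain no on-treatment value and, for most of these endpoints, not even the endpoint's own baseline. A likelihood-based repeated-measures model makes a weaker assumption: non-completion may also depend on the values already recorded, including those at weeks 5 and 9. At stake are the biomarker and cardiometabolic comparisons that the protocol lists as specific objectives.

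**Working it through.** **Inputs.** Randomised 42 and 46; discontinued 1 and 6; removed 0 and 1; completed 41 and 39 (all SAP). Visits and endpoints are as above (protocol).

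**1. Reproduce the flow.** 88 − 7 − 1 = 80; 42 − 1 = 41; 46 − 6 − 1 = 39. The SAP's figures agree.

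**2. Non-completion.**
- DAPA+MET: 1/42 = 2.4%.
- MET: 7/46 = 15.2%, made up of 6/46 = 13.0% discontinued and 1/46 = 2.2% removed.
- Overall: 8/88 = 9.1%.
- Fisher exact p for the imbalance is 0.06, or 0.11 counting discontinuations only.

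**3. Standard error of the arm difference, in SD units.**
- Completers: √(1/41 + 1/39) = 0.2237.
- Final values from all 88: √(1/42 + 1/46) = 0.2134.
- Ratio: 0.2237/0.2134 = 1.048. This is a ceiling, because interim values do not replace a final value fully.

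**4. What interim values can recover.** Assume equal correlation ρ between post-baseline visits. In an arm with N randomised and n completers, where every non-completer has the interim values stated, the variance of the last-visit mean in SD² units is

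R²/N + (1 − R²)/n,

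where R² = ρ² if only week 5 is recorded and R² = 2ρ²/(1 + ρ) if weeks 5 and 9 are. Example with ρ = 0.5 and week 5 only (R² = 0.25):
- MET: 0.25/46 + 0.75/39 = 0.02467.
- DAPA+MET: 0.25/42 + 0.75/41 = 0.02425.
- Standard error: √0.04891 = 0.2212, which is 1.1% below 0.2237.

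| Assumed ρ | No interim value | Week 5 only | Weeks 5 and 9 |
|---|---|---|---|
| 0.3 | 0% | −0.4% | −0.6% |
| 0.5 | 0% | −1.1% | −1.5% |
| 0.7 | 0% | −2.2% | −2.6% |
| 0.8 | 0% | −2.9% | −3.2% |

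**5. Possible bias.** If non-completers' outcomes differ from completers' by d SD, equally in both arms (assumed), the completers-only contrast shifts by d × (7/46 − 1/42) = 0.128 d.

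| Assumed d | Shift (SD) | Share of the 0.2237 standard error |
|---|---|---|
| 0.25 | 0.032 | 14% |
| 0.5 | 0.064 | 29% |
| 1.0 | 0.128 | 57% |

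Counting the six discontinuations alone, the multiplier is 6/46 − 1/42 = 0.107.

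**The case against.** The strongest reply is that the benefit depends on a fact the documents do not give. The SAP reports neither when nor why patients left. If they left before week 5, a model on post-baseline visits omits them too and recovers nothing. That stands, so the benefit must be stated as conditional and the counts reported.

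Second, a reader might infer that 15% of MET patients were lost before the last visit. The documents do not support this. One of the seven was removed for non-compliance, partly with CGM instructions, and CGM runs at the start and at the end, so this patient may have reached the final visits. Removal is a decision about the analysis population, and a mixed model does not reverse it unless the population is also defined.

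Third, a reader might infer that the plan prescribes a complete-case analysis in which non-completers contribute nothing. It does not say so. That follows from the change-score definition together with the absence of any missing-data rule.

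Fourth, the SAP is written with patient flow and baseline comparisons already known. Replacing the planned ANCOVA now would be a post hoc switch. This also stands: the new model belongs beside the planned analysis, not in its place.

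Finally, only secondary outcomes are touched, and the sample size was not set for them. True, but they are named objectives, the extra measurements are already scheduled, and a reader cannot otherwise judge how far unequal non-completion affects them.

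**Conclusion.** The concern holds for antioxidant capacity, VCAM-1, adiponectin, weight, blood pressure and body fat. Their week-5 and week-9 values have no analytic use, there is no missing-data rule, and non-completion was 2.4% against 15.2%.

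The size is moderate. The standard error would fall by 0% to about 3%, for assumed correlations of 0.3 to 0.8 and depending on which interim values exist. The 5% suggested by comparing 80 with 88 patients would need final values from everyone. The main aim is less bias: a shift of about 0.03 to 0.13 SD if non-completers differ by 0.25 to 1.0 SD. The mixed model removes only the part predictable from recorded values, and it still assumes missingness at random.

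A reader might go further and conclude that the secondary results are biased, or that the primary result is. Neither follows. The documents give no reasons for leaving and no outcomes of non-completers, and MAGE has no interim measurement for such a model to use.

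**What to change.** 1. For the six endpoints named, fit a linear mixed model (SPSS MIXED) on all post-baseline visits. Include every randomised patient with at least one post-baseline value, in the assigned arm, and include the removed MET patient where values exist. Terms: arm, visit, arm × visit, the planned covariates and the endpoint's own baseline, with unstructured covariance. Report the arm contrast at the last visit. Log-transform markers that are skewed.
2. Keep the planned change ANCOVA, add the endpoint's own baseline to it, and report the two side by side.
3. Because patient flow is already known, record the change through the protocol's procedure for deviations from the statistical plan, which is a letter to the research committee for approval.
4. Report by arm how many non-completers have a week-5 or week-9 value. If none has, say that the model adds nothing for them.
5. State whether the protocol's exclusion of patients with an acute stress event, justified there by its effect on glycemic variability, applies to these endpoints.
6. Include insulin only once its schedule is reconciled: the text gives 1DP and 6DP, while the table also marks 3DP and 4DP. Its baseline of 12.2 ± 13.3 µU/mL in DAPA+MET also suggests skew. HbA1c has a similar conflict, since the table adds 3DP.
7. Leave the MAGE analysis as it is on this point.

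The cost is a paragraph in the SAP, a few lines of syntax, one count from existing records and the committee letter. No new data are needed. The price is a missing-at-random assumption, which is weaker than what a completers-only comparison requires.
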